8.2.4.3. Survival time

For the period from the start of administration of this drug to the end date of the observation period, the number and proportion of patients experiencing death of any cause and deaths related to cardiovascular events will be tabulated separately. In addition, each event will be summarized as described in Section 8.1.4. In the analysis in Section 8.1.4, data will be censored at the last date of confirmation of survival. If the date of death is unknown and the last date of confirmation of survival and date of death information obtained are known, data will be handled as interval censored. The handling of patients in the survival analysis is outlined below.

Non-English text

8.2.4.4. Exploratory analysis

For each of the factors specified in Section 5.4, subgroup analyses will be performed for the efficacy analyses described in Section 8.2.4. Kaplan-Meier estimation will be used to analyze the survival time by using the factors shown in Section 5.4 as stratification variables.

Additional analyses may be performed as necessary. The exploratory analysis will be reported only when results giving important interpretation are obtained.

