5.4. Subgroups

Subgroup analyses of safety will be performed for the following patient characteristics and other factors. For the patient characteristics and other factors with those of specific categories underlined, a risk ratio will be calculated using each underlined category as the reference.

- Inpatient/outpatient status at the first prescription [inpatient, outpatient]
- *Severity of liver impairment [absent, mild, moderate, severe]
- Liver impairment [absent, present]
- Renal impairment [absent, present]
- Age [<15 years, ≥15 to <65 years, ≥65 years]
- *TTR genetic variant [wild-type, variant]
- NYHA functional classification [Class I/II, III/IV]
- NYHA functional classification [Class I, II, III, IV]
- Concomitant medication [absent, present]
- Non-drug therapy (device therapy) [absent, present]

- Complication [absent, present]
- Gender [male, female]
- Usage experience of this drug (administered this drug for the first time, transferred from clinical trials, transition from the treatment of ATTR-PN)

*Evaluation of the important missing information (safety in patients with severe liver impairment and patients with variants)

Subgroup analyses of efficacy will be performed for the following patient characteristics:

- TTR genetic variant [wild-type, variant]
- NYHA functional classification [Class I/II, III/IV]
- NYHA functional classification [Class I, II, III, IV]

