8.1.4. Analysis of period data (time to event onset)

The median, first quartile, and third quartile will be calculated by the Kaplan-Meier method. For period data which includes interval-censored data, the median, first quartile, and third quartile will be calculated based on the EMICM algorithm. In addition, Kaplan-Meier plots will be prepared.

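### Undated deaths are interval-censored and go to EMICM for the quartiles, but the survival plots and subgroup survival are specified as Kaplan-Meier, which cannot take them

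*SAP*

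**What the plan says.** Survival time is an efficacy endpoint (SAP 6.2), covering death from any cause and cardiovascular death. Four statements decide how it is estimated.

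- **SAP 8.2.4.3, general rule:** "data will be censored at the last date of confirmation of survival".
- **SAP 8.2.4.3, undated deaths:** "If the date of death is unknown and the last date of confirmation of survival and date of death information obtained are known", then "data will be handled as interval censored". An outline of how patients are handled follows, but it appears in the public text only as a placeholder for non-English content.
- **SAP 8.1.4, estimator:** Kaplan-Meier by default, with an exception: "For period data which includes interval-censored data, the median, first quartile, and third quartile will be calculated based on the EMICM algorithm". The next sentence has no exception: "In addition, Kaplan-Meier plots will be prepared".
- **SAP 8.2.4.4, subgroups:** the first sentence says that "subgroup analyses will be performed for the efficacy analyses described in Section 8.2.4". The sentence on survival then reads "Kaplan-Meier estimation will be used to analyze the survival time by using the factors shown in Section 5.4 as stratification variables". For efficacy, the Section 5.4 factors are TTR type (wild-type or variant), NYHA I/II against III/IV, and the four NYHA classes.

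**The concern.** The plan defines a kind of observation, a death known only to lie between two dates, and then names for the curves and subgroups an estimator with no place for it. The Kaplan-Meier estimator needs each time to be either exact or right-censored. To put an interval-censored death into it, the analyst must assign a date, drop the patient, or treat the patient as alive and censored. These choices give different answers, and the readable text does not choose among them.

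At stake is the consistency of one endpoint within one report. The quartiles would use every death, while the plotted curve and the TTR and NYHA results might not. A report could print an EMICM first quartile that its own curve never reaches. The analyst would also be choosing the handling with the data in hand.

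**Working it through.** **1. The text side by side.**

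| Output | Estimator named | Takes interval-censored deaths? |
|---|---|---|
| Median and quartiles (8.1.4) | EMICM when such data are present | Yes |
| Survival plot (8.1.4) | Kaplan-Meier, no exception | No |
| Survival by TTR type and NYHA class (8.2.4.4, survival sentence) | Kaplan-Meier | No |

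The documents state no mortality, no survival figure and no count of undated deaths, so there is no survival figure of the plan's own to reproduce. Everything below rests on assumed inputs, except the target of 300 patients (protocol 8.5.1) and the 30 months of observation (protocol 8.2.6).

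**2. Size if undated deaths are censored at the last date known alive.** Assume a constant hazard, 30-month mortality m and a fraction u of deaths undated. The hazard is h = −ln(1 − m)/30. Censoring a fraction u of the deaths leaves an apparent hazard of h(1 − u), so the curve at month 30 is exp(−30h(1 − u)) = (1 − m)^(1 − u). The shift is that value minus (1 − m). The standard error for 300 patients is √(m(1 − m)/300).

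For m = 0.25 and u = 0.10: 0.75^0.9 = 0.772, a shift of 2.2 points; SE = √(0.1875/300) = 2.5 points.

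| m | u = 5% | u = 10% | u = 20% | SE, n = 300 |
|---|---|---|---|---|
| 15% | 0.7 | 1.4 | 2.8 | 2.1 |
| 25% | 1.1 | 2.2 | 4.4 | 2.5 |
| 35% | 1.4 | 2.9 | 5.8 | 2.8 |

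(Shifts and SEs in percentage points.)

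**3. Size if the patients are dropped.** Ignoring other censoring, survival becomes (1 − m)/[(1 − m) + m(1 − u)]. At m = 0.25 and u = 0.05, 0.10 and 0.20 this is 0.759, 0.769 and 0.789, so the shifts are 0.9, 1.9 and 3.9 points.

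**4. Size if a date is imputed.** This was simulated with 300 patients, exponential death times and true 30-month survival of 60%, 70% or 80%. A quarter of patients were given a random earlier censoring time. The bounds on an undated death lay up to 3 months either side of the true date, with the upper bound cut at month 30. There were 15 data sets per setting, and 25 for the quartile comparison. The interval-based nonparametric estimate, which is what EMICM targets, matched Kaplan-Meier on the full true dates at month 30 to within about 0.001. So did Kaplan-Meier with the date set to the left, middle or right of the interval. Because every interval closed by month 30, this near-zero result applies at month 30; imputation can still shift the curve before then.

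**5. Disagreement with the quartiles.** In the same simulation, at 70% true survival:

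| n, share undated | 30-month survival: interval-based / Kaplan-Meier, censored | First quartile (months): interval-based / Kaplan-Meier, censored |
|---|---|---|
| 300, 5% | 0.698 / 0.710 | 23.9 / 25.4 |
| 300, 20% | 0.704 / 0.755 | 24.9 / 29.9 |
| 40, 20% | 0.711 / 0.759 | 28.7 / not reached in most data sets |

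With 300 patients and 20% undated, the interval-based estimate reached a first quartile in every data set, and Kaplan-Meier with censoring in 52% of them.

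**6. Yardstick in subgroups.** For an illustrative subgroup of 40 at m = 0.25, SE = √(0.1875/40) = 6.8 points. The 2.2-point shift is then 2.2/6.8, about a third of a standard error, against 2.2/2.5, about 0.9, in the whole cohort.

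**The case against.** A reader might infer that the SAP itself tells the analyst to censor undated deaths at the last date known alive, so that the curves will lose those deaths. The text does not say that. Section 8.2.4.3 gives the censoring rule first and then a separate rule for undated deaths with both bounds known. Censoring is one handling an analyst might fall back on, not an instruction, so the shifts in steps 2 and 3 are conditional.

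Four further points stand.

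- The outline after 8.2.4.3 is where handling of these patients might be shown. It is unreadable here and cannot be counted as absent from the plan.
- The first sentence of 8.2.4.4 repeats the 8.2.4 analyses by subgroup. It can be read as carrying 8.1.4, and so EMICM, into the subgroups, with the Kaplan-Meier sentence adding only the strata. It is therefore too strong to say that all subgroup survival is Kaplan-Meier with no alternative. The SAP change log is compatible with leftover wording: version 5.0 records the interval-censoring addition to 8.1.4 and names no change to 8.2.4.4. That is inference.
- Undated deaths may be few. Date of death is a CRF item (protocol 8.3.7), deaths are serious adverse events reportable within 24 hours of awareness (protocol 10.1 and 10.4.2), and transferred patients are linked across sites (protocol 8.2.6). A suggestion that undated deaths fall unequally across TTR or NYHA groups has no support in the documents.
- The study is non-confirmatory (SAP 4), no decision rule depends on the curves, and deaths are also tabulated as counts and proportions.

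None of this removes the mismatch. On any reading, the plot sentence in 8.1.4 has no exception for interval-censored data, and the survival sentence in 8.2.4.4 names an estimator that cannot use such data as they stand.

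**Conclusion.** The plan is inconsistent about the estimator for one endpoint: EMICM for the quartiles when dates are missing, Kaplan-Meier for the plot and, on the plain reading of its survival sentence, for the TTR and NYHA subgroups. The plotted and subgroup survival may therefore disagree with the EMICM quartiles.

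The documents do not support a statement that survival will be overstated. At month 30 the effect runs from about zero, if dates are imputed, to an upward shift if undated deaths are censored or dropped. For censoring, the shift is about 1 to 4 points at an assumed 25% mortality with 5% to 20% of deaths undated, against a standard error of 2.5 points in 300 patients. The 300 is the target for the safety analysis set; the efficacy set is drawn from it, and in subgroups the standard error is larger and the shift correspondingly less conspicuous. This is worth correcting because the correction costs almost nothing, although the analysis is exploratory.

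**What to change.** Three small changes to the SAP:

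1. In 8.1.4, state that when any interval-censored time is present, the plotted curve is the nonparametric EMICM (Turnbull) estimate. Kaplan-Meier stays where all times are exact or right-censored.
2. In 8.2.4.4, replace the words naming Kaplan-Meier estimation with a reference to the method of 8.1.4, so that each subgroup follows the same rule as the overall analysis.
3. Report the number of interval-censored deaths overall and by subgroup, so that the reader can see whether the choice matters.

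If the outline after 8.2.4.3 already sets a rule for these deaths in the Kaplan-Meier curves, the text of 8.1.4 and 8.2.4.4 should be brought into line with it.

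The cost is two reworded sentences and one added count. The algorithm is already planned and yields the curve. The downside is slightly more programming and a less familiar curve.

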9. LISTINGS

The following listings will be prepared:

- Listing of patients
- Listing of patients experiencing adverse events
- Listing of patients experiencing adverse reactions
- Listing of patients excluded from the safety analysis experiencing adverse reactions
- Listing of patients with a contraindication experiencing adverse reactions
- Listing of patients experiencing serious adverse reactions
- Listing of patients experiencing serious adverse events
- Listing of patients with TTR variants experiencing adverse reactions
- Listing of patients with severe liver impairment experiencing adverse reactions
- Listing of patients with renal impairment experiencing adverse reactions
- Listing of patients experiencing adverse reactions resulting in dose reduction
- Listing of pediatric patients (aged <15 years) experiencing adverse reactions
- Listing of elderly patients (aged ≥65 years) experiencing adverse reactions
- Listing of adverse reactions by safety specification
- Listing of laboratory test values
- Listing of efficacy evaluations

In addition, a form necessary for reexamination application (PSEHB/PED Notification No. 1128-2 dated November 28, 2017 issued by the Director of Pharmaceutical Evaluation Division, Pharmaceutical Safety and Environmental Health Bureau, Ministry of Health, Labour and Welfare) will be prepared.

Furthermore, a form necessary for Periodic Safety Update Reports (PSEHB/PED Notification No. 1128-5 and PSEHB/SD Notification No. 1128-4, dated November 28, 2017 issued jointly by the Director of Pharmaceutical Evaluation Division and the Director of Safety Division, Pharmaceutical Safety and Environmental Health Bureau, Ministry of Health, Labour and Welfare) will be prepared.

11. APPENDICES

11.1. Appendix 1: Details of Data Extraction

A1.1 Definition of Efficacy Evaluation Time Points

Visit time	Endpoints	Definition [Time window]
At baseline	Laboratory tests, efficacy endpoints	Between 30 days before the first date of administration (start date of administration) and the start date of administration in this study. For NYHA functional classification, the evaluated value of NYHA functional classification entered in the "Target disease" page of the case report form will be adopted.
Month 6	Laboratory tests, efficacy endpoints	Between 3 months and 9 months after the start of administration
Month 12	Laboratory tests, efficacy endpoints	Between 9 months and 15 months after the start of administration
Month 18	Laboratory tests, efficacy endpoints	Between 15 months and 21 months after the start of administration
Month 24	Laboratory tests, efficacy endpoints	Between 21 months and 27 months after the start of administration
Month 30	Laboratory tests, efficacy endpoints	Between 27 months and 39 months after the start of administration
At discontinuation	Laboratory tests, efficacy endpoints	1 month before or after the last date of administration in this study

If there are multiple values of the same endpoint at the same visit time, the value measured on the closest day to each visit time will be adopted. If there are multiple values measured on the closest day, the value measured at a later date will be adopted.

11.2. Appendix 2: Example of Risk Ratios of Subgroups to the Incidence of Adverse Reactions

Non-English text

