#### **8.2.6. Observation period**

[figure not shown]
30 months (Week 130) from the start of administration (Day 1)

However, for patients who discontinued this drug during the observation period, the observation period will be until the first visit after the date of discontinuation.

[figure not shown]
In this study, information will be collected using a booklet type CRF. Information during the following periods will be entered in each booklet.

If the patient is transferred to another hospital or department (hereinafter referred to as hospital transfer) during the observation period, the patient will be newly registered even at the transferred site and the CRF will be completed. If the patient is transferred to another hospital, the patient registration number of the original site will be conveyed to the transferred site. Although the patient will be given a new patient registration number at the transferred site at the time of registration, he or she will be determined to be a transferred patient by reporting the patient registration number of the original site and his/her data will be handled as the same patient. If the time point of 30 months after the start date of initial administration can be identified for the transferred patient, the observation period at the transferred site may be reset so that the total observation period of the patient in this study will become 30 months.

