### **8.3.4. Tests/clinical laboratory tests**

#### **8.3.4.1. Clinical laboratory tests**

The results of tests performed before the start date of administration (including the start date of administration) and during the observation period of each booklet (or until the first visit date after the date of discontinuation of this drug) should be recorded. If the abnormal value is clinically significant compared to the value before dosing, this information should also be recorded in detail in the adverse event field.

1. NT-proBNP

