#### 8.3.4.2. Clinical symptoms

The following clinical symptoms should be recorded at the start of administration, Week 52, Week 130, and at the time of discontinuation.

- NYHA Functional Classification

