#### 8.3.6. Implementation status of the study and records at discontinuation

The administration status of this drug at the end point of observation period in each booklet should be confirmed. If the patient discontinued the administration of this drug by the end point of observation period in each booklet, data at the first visit after the date of discontinuation should be recorded regardless of the reason for discontinuation. If the administration of this drug is continued, it should be entered as completed. If the administration is discontinued, only one of the following primary reasons should be selected. If the primary reason for discontinuation is an adverse event or others (abnormal laboratory test value), necessary information should be recorded in the adverse event field.

1. End date of the observation period (or the date of the first visit after the date of discontinuation)

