7. HANDLING OF MISSING DATA

If treatment with this drug is continued even after the end of the observation period and the end date of treatment is missing, the end date of observation will be handled as the end date of treatment in this study.

If the seriousness, causal relationship, and action taken and outcome regarding adverse events are missing, these data will be handled as “unknown” for tabulation.

For the efficacy endpoints and laboratory test values, if there is no measurement within the time window for each evaluation time point (Appendix 1), data will be handled as missing, and the missing data will not be complemented.

The strategy for handling data with uncompleted cleaning is described below:

- Items of missing data: The items will be handled as missing (category of categorical variables is “unknown”) for both tabulation and listing.
- Items of inconsistent data: The items will be handled as missing for both tabulation and listing. However, a list of data handling should be prepared separately.
- No signature: Any entry in a case report form without the signature of the contracted physician (including a case report form with the signature of an uncontracted physician only) will be handled as missing for both tabulation and listing. If there is no date of signature in the field for the date of signature or if there is inconsistency in the date entered (e.g., date before the start date of treatment, future date), the entry in the case report form will be regarded as having no signature.

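### The 1-month window for the discontinuation time point drops first-visit values that the protocol collects for it, and the SAP does not say which patients the row covers

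*SAP*

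**What the plan says.** **Collection (protocol).**
- Section 8.2.6: for a patient who stops, "the observation period will be until the first visit after the date of discontinuation". No maximum delay is given.
- Section 8.3.6: "data at the first visit after the date of discontinuation should be recorded regardless of the reason for discontinuation". The date of that visit is itself a recorded item.
- Section 8.3.4.1: biomarkers are recorded during each booklet's observation period, "or until the first visit date after the date of discontinuation of this drug".
- Section 8.3.4.2: NYHA class is recorded "at the start of administration, Week 52, Week 130, and at the time of discontinuation".
- Section 8.3.6 also separates patients still on treatment: "If the administration of this drug is continued, it should be entered as completed". The other status options include transfer to another hospital or department.

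**Analysis (SAP).**
- Appendix 1, A1.1, defines the discontinuation time point as "1 month before or after the last date of administration in this study". The row names no population. Where several values qualify, the one nearest the time point is taken.
- Section 7: "if there is no measurement within the time window for each evaluation time point (Appendix 1), data will be handled as missing", and nothing is imputed.
- Section 7 also provides that, for a patient who continues treatment past observation and has no end date, "the end date of observation will be handled as the end date of treatment in this study".
- Sections 8.2.4.1 and 8.2.4.2 summarise NYHA class and four biomarkers at discontinuation, among other time points.

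**The concern.** The protocol defines the discontinuation record by an event, the next visit. The SAP defines it by a calendar distance from the last dose. When the next visit is more than 1 month away, the value collected for this purpose no longer qualifies.

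The window is also tight compared with its neighbours. Months 6 to 24 each allow 3 months either side, and Month 30 runs from 27 to 39 months. The narrowest post-baseline window is applied to the one visit whose timing the protocol leaves open.

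Discontinuation is one of three post-baseline time points for NYHA class and one of three for the descriptive biomarker change from baseline. In an uncontrolled study, status at stopping is useful context, and the SAP does not plan to report how many first-visit values the window excludes.

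A second, smaller matter is who belongs in the row. It is anchored on the last administration date, and section 7 can give continuing patients such a date.

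**Working it through.** The plan gives no figure for this point: no visit interval, no discontinuation rate and no expected number of values at discontinuation. What follows compares the rules and then applies simple proportions to assumed spacings. The date of discontinuation is taken to coincide with the last administration.

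**Step 1. First visits outside the limit.** Let routine visits be *v* months apart (assumed) and let stopping times be uniform between visits. The next visit is then uniform on 0 to *v* months after the last dose, and the share more than 1 month away is max(0, 1 − 1/*v*).

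**Step 2. Discontinuers with no value in the window.** The window is two-sided, and biomarkers may be measured before stopping. If there is a measurement at every visit, a patient has no qualifying value only when the previous visit was more than 1 month before the last dose and the next is more than 1 month after it. The share is max(0, 1 − 2/*v*).

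| Assumed spacing *v* (months) | First visit outside limit, 1 − 1/*v* | No value in window, 1 − 2/*v* (biomarkers, every visit) |
|---|---|---|
| 1 | 0% | 0% |
| 2 | 50% | 0% |
| 3 | 67% | 33% |
| 6 | 83% | 67% |

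The first column counts first-visit values that cannot be used. The second counts patients left with nothing. The second is the relevant loss for biomarkers, if they are measured at each visit.

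**Step 3. NYHA class.** NYHA is scheduled only at start, Week 52, Week 130 and discontinuation, so a value shortly before stopping will often not exist and the first column is the closer guide. A late first-visit NYHA value can still be tabulated if it falls in the Month 12 window (9 to 15 months) or the Month 30 window (27 to 39 months). If it falls before Month 9 or between Months 15 and 27, it enters no NYHA table. Those stretches make up 9 + 12 = 21 of the 30 months. The value then appears only in the listing of efficacy evaluations (SAP section 9).

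**Step 4. The nearest-value rule.** Even when the first visit is within 1 month, a measurement taken before the last dose and closer to it would be chosen instead.

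**Step 5. The population of the row.** For a patient still on drug with no end date, section 7 puts the end of treatment at the end of observation. Week 130 is 130 × 7 = 910 days, or 910/30.4375 = 29.9 months. One month either side gives about 28.9 to 30.9 months, wholly inside the Month 30 window. Read literally, the same value could count at both time points. If no filter were applied, data availability were equal, and 20%, 30% or 50% of 300 patients stopped (assumed), completers would make up 240/300 = 80%, 210/300 = 70% or 150/300 = 50% of the row. With a filter on recorded status the figure is 0%.

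**The case against.** **A window near the last dose is a defensible choice.** Protocol 8.3.4.2 itself speaks of the time of discontinuation, and protocol 8.7 leaves detailed methods to the SAP. A value taken many months off drug is a poor description of status at stopping. This stands as a reason to show the time gap and to keep a 1-month summary as a check. It does not explain why data collected under the protocol's rule should be set to missing without being counted.

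**Late biomarker values are not lost from the analysis altogether.** The scheduled windows run without a break from Month 3 to Month 39 and carry no on-treatment restriction, so a late value may enter a scheduled summary or the MMRM. The individual plots use every measured value. This stands for biomarkers; for NYHA class it holds only in part (Step 3).

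**Completers.** A reader might infer that the discontinuation summaries will describe the wrong patients. The documents do not support that. The row is labelled for discontinuation, the CRF has a separate completed status, SAP 8.2.1.2 tabulates discontinuations on their own, and no text says completers will be included. The section 7 rule has an evident use in tabulating treatment periods. What remains is that the SAP does not state the filter. Recorded status is also not a clean filter: transfer is among the non-completed options, and SAP 2.1 says prescription may continue at the new site.

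**Direction of bias.** A reader might also infer that the rule makes status at stopping look better because the sickest patients are lost. Nothing in the documents shows this. The listed reasons for stopping include recovery and transfer, and a patient with a late first visit has survived to attend it.

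**Conclusion.** The mismatch between the protocol's collection rule and the SAP's window is plain in the text. First-visit values more than 1 month after the last dose drop out of the discontinuation time point, and the effect is greatest for NYHA class.

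The amount cannot be fixed from the documents. At assumed spacings of 1, 2 and 3 months with uniform stopping times, 0%, 50% and 67% of first visits are outside the limit. For biomarkers measured at every visit, 0%, 0% and 33% of discontinuers have no usable value. The loss may be nil.

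The unstated population of the row is a wording gap, and no direction of bias is established.

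The reach is limited to the descriptive NYHA and biomarker summaries at discontinuation, including their subgroup versions. The MMRM has no discontinuation time point, and the survival and safety analyses do not use this window. The study is declared non-confirmatory (SAP section 4). It is worth correcting because the data are already collected and the remedy is small.

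**What to change.** In SAP Appendix 1, A1.1:

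1. Limit the discontinuation row to patients recorded as having stopped the drug, and state how patients who transferred hospital while still on drug are treated.
2. Use the value recorded at the first visit after discontinuation. If there is none, use the last value within 1 month before the last dose. State that this order replaces the nearest-value rule for this row.
3. Report the distribution of days from last dose to the value used.
4. Show the same summary restricted to values within 1 month of the last dose as a sensitivity check.

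The cost is a change to SAP wording and one derivation. No new data are needed, since the date of the first visit after stopping is already on the CRF. The downside is that some values will lie further from the last dose; items 3 and 4 make that visible.
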